9.7. Randomisation

Participants will be randomised by the site study team after the baseline visit and before primary hospital discharge, using a secure web-based randomisation system provided by the Oxford Primary Care Clinical Trials Unit. If a participant has been discharged from hospital before being randomised the research midwife will contact the participant and carry out remote consent and randomisation over the phone within 7 days of being discharged. The system will allow for the allocation of participants to the two

randomisation groups: usual care or self-management on a 1:1 basis and for this allocation to be stratified according to recruitment site with minimisation for principal diagnosis (chronic hypertension or gestational hypertension/pre-eclampsia), and mean postnatal diastolic blood pressure (last 3 readings in clinical record, <83mmHg vs \geq 83mmHg), and number of antihypertensive medications (<2 vs \geq 2 medications).

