11.1.1 Description of the Statistical Methods

All analyses will be conducted in accordance with Oxford Primary Care CTU SOPs.

Internal pilot: Descriptive statistics will be used to describe recruitment of the first 100 participants (section 9.12).

In accordance with CONSORT guidelines, we will record and report participant flow. Descriptive statistics of recruitment, drop-out/withdrawal and completeness of intervention will be reported.

Baseline variables will be presented by randomised group using frequencies (with percentages) for binary and categorical variables and means (standard deviations) or medians (with lower and upper quartiles) for continuous variables. There will be no tests of statistical significance nor confidence intervals for differences between groups on any baseline variables.

The primary estimand is the mean difference in daytime ambulatory diastolic BP at 22-39 weeks for all randomised participants, as defined by protocol eligibility criteria, regardless of what intervention they actually received or adherence of intervention. A generalised linear mixed-effects model utilising data collected all time-points from randomisation will be fitted to the data with mean daytime diastolic BP measured at 22-39 weeks as the response variable, adjusting for minimisation factors for principal diagnosis (chronic hypertension or gestational hypertension/pre-eclampsia), mean postnatal diastolic blood pressure (last 3 readings in clinical record) ($<83/\ge83$), number of anti-hypertensive medications ($<2/\ge2$) and randomised group fitted as fixed effects and the model will include site as a random effect. An adjusted mean difference at 22-39 weeks between the randomised groups, together with a 95% confidence interval and a P value, will be estimated from the model.

A similar approach will be used for continuous secondary outcomes, and generalised linear model for binary outcomes. Time effects will be included in the model for repeated measures outcomes where appropriate.

Safety outcomes will be compared using Fisher's exact or Chi-square test.

Pre-specified subgroup analyses of the primary outcome will be explored by baseline diastolic BP, principal diagnosis, ethnicity, indices of multiple deprivation quintiles, social status, and parity.

Standard residual diagnostics will be assessed for the appropriateness of the model.

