11.2. Sample Size Determination

Using data from the SNAP-HT feasibility trial and its follow-up study (Cairns AE, 2017), it is estimated that the standard deviation of mean daytime ambulatory diastolic BP at 6 months will be 10mmHg (inflated from 8mmHg to take into account greater heterogeneity between recruiting sites in this multicentre trial); 314 women (157 per group) are needed to detect ≥4mmHg difference (standardised difference 0.4) with alpha 0.05 and 90% power, and 15% post-randomisation drop out.

The aim will be to recruit approximately similar numbers of women with gestational hypertension/pre-eclampsia and chronic hypertension meaning that 628 women will be included overall. Assuming that the heterogeneity between these groups is small enough, 80% power will be retained for at least 5mmHg difference in diastolic BP for sub-groups of at least 40% of the total sample size, e.g. white vs non-white (expected 60:40 proportions). Furthermore, if appropriate to combine, the full sample of 628 women would allow smaller effect sizes to be detected (effect size = 0.22 - 80% power, effect size = 0.26 - 90% power).

During the regular monitoring of the trial, the TMG noted a higher proportion of gestational hypertensive women were enrolled in the study, (approximately 80%). In addition, the monitoring of ABPM completion showed low completion rates of ABPM (<50%). The sample size was subsequently inflated for operational reasons to retain the pre-specified power in the original sample size calculation in both gestational and chronic hypertensives as far as possible. Therefore, the sample size was updated to ensure 532 (266/0.5) gestational hypertensive women would be randomised and the remaining chronic hypertensive women to be recruited as far as possible in the recruitment period. Thus the recruitment period will allow approximately a total of 690 women.

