11.6. The Level of Statistical Significance

The level of significance will be set at 5% two-sided significance level. P-values will be adjusted for any multiple comparisons in order to maintain an overall type I error rate of 5%.

11.7. Procedure for Accounting for Missing, Unused, and Spurious Data.

Missing data in all outcomes will be inspected and reported, with reasons given where available and missing data mechanism explored across randomised groups. We will explore the mechanism of missing data, though the mixed effects model implicitly accounts for data missing at random. Factors found to be predictive of missingness will be included as fixed effects in the analysis models.

Additional sensitivity analysis using imputation methods, such as multiple imputation for data missing will be performed and a pattern mixture model for longitudinal data will be fitted to assess the robustness of the missing at random assumption required for mixed effect models.

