16.4. Other Ethical Considerations

The main ethical issues associated with this research are confidentiality, informed consent, ensuring that participation does not lead to inferior care and ensuring women are not inappropriately contacted following still birth or any other poor outcome.

Confidentiality of potential participants in the programme will be maintained through scrupulous data management and careful communication.

Consent will be taken only after potential participants have had an opportunity to consider whether to take part in the study and randomisation will occur after birth. Women will be supported to make an informed choice and can be approached prior to birth if appropriate. Women will be free to discontinue or amend their participation in the study at any stage. Importantly, all interventions will be in addition to standard care so no participating women will receive inferior care compared to usual care.

Women in both randomisation groups will receive postnatal management by their community midwife and GP following their discharge from hospital. If women in the intervention arm still require additional support from the GP or community midwife postpartum for other medical, mental health or social issues then this will continue irrespective of their involvement in the trial.

Any incidental findings that arise as a result of study procedures or investigations will be communicated directly to participants by the site PI or CI. With a participant's consent these findings will be passed on to the participant's GP so that appropriate follow up can be arranged if required.

Women who suffer an adverse perinatal outcome (Neonatal Unit admission, intrauterine fetal death or neonatal death) will not be automatically excluded from the study, but there will be careful consultation with the midwifery and obstetric teams before these women are approached, and the approach will be considered sensitively. This follows direct advice and input from lay representatives who have experienced such outcomes.

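### Safety is compared between arms by a significance test alone; for uncommon harms a risk difference with a 95% confidence interval would tell the reader more

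*Protocol*

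**What the plan says.** Protocol section 11.1.1 describes the between-arm comparisons. For the primary outcome it asks for an adjusted mean difference with a 95% confidence interval and a P value. Continuous secondary outcomes follow a similar approach, and there is a "generalised linear model for binary outcomes". Safety has a single sentence: "Safety outcomes will be compared using Fisher's exact or Chi-square test".

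Other parts of the protocol that bear on this:

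- **Size and allocation.** Section 11.2: "Thus the recruitment period will allow approximately a total of 690 women". Section 9.7 allocates women to "usual care or self-management on a 1:1 basis".
- **Significance.** Section 11.6: "The level of significance will be set at 5% two-sided significance level". The same section adjusts P values for multiple comparisons and does not say whether safety tests are included.
- **Events.** Section 10.4 lists expected serious events, including very high or low blood pressure, faints and falls. It says they are captured as outcomes and need no SAE report. Section 6 lists admissions and cardiovascular events as secondary outcomes.
- **Oversight.** Section 10.3 sends all SAE reports to the data monitoring committee.
- **Ethics.** Section 16.4 names, among the main issues, "ensuring that participation does not lead to inferior care".

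**The concern.** A Fisher's or chi-square test gives a P value. It does not give the size of any excess risk or an upper limit for it. That matters most where a trial has little power, and this trial was sized for a 4 mmHg difference in a mean, not for event rates. For an uncommon harm, P above 0.05 is the likely result both when self-management is harmless and when it doubles the risk.

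The intervention guides changes in antihypertensive medication from self-measured readings. Section 10.4 itself marks low blood pressure on treatment, faints and falls as potentially related to blood pressure management. A reader will want to know what excess of such events the trial has ruled out, and the safety sentence as written does not ask for that number.

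It is also unclear which method covers the section 10.4 events. Since they are captured as outcomes, they could fall under the safety sentence or under the model for binary outcomes.

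**Working it through.** **Step 1. The plan's own figure.** The protocol states no power or precision for safety, so its only sample-size figure is the one for the primary outcome. Section 11.2 says "it is estimated that the standard deviation of mean daytime ambulatory diastolic BP at 6 months will be 10mmHg", with a 4 mmHg difference, 90% power and 15% drop-out. A two-sample t-test with standardised difference 4/10 = 0.4 and two-sided alpha 0.05 needs 133 per arm (266 in all). Then 133/0.85 = 156.5, rounded up to 157 per arm, or 314. This reproduces. So does the revised target of 266/0.5 = 532 women with gestational hypertension.

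**Step 2. Inputs for safety.**

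- From the protocol: about 690 women at 1:1, so 690/2 = 345 per arm; two-sided 5%.
- Assumed, because the protocol gives no event rates: a usual-care risk *p* of 1% to 10%, a true doubling to 2*p*, every woman observed, and no multiplicity adjustment.

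**Step 3. Power.** For each pair of event counts (*i*, *j*), the probability is Bin(*i*; 345, *p*) × Bin(*j*; 345, 2*p*). Power is the sum of these probabilities over all pairs with a test P value of at most 0.05. The miss rate is 1 − power.

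| Usual care vs self-management | Fisher power | Fisher misses | Uncorrected chi-square misses |
|---|---|---|---|
| 1% vs 2% | 11% | 89% | 82% |
| 2% vs 4% | 27% | 73% | 66% |
| 3% vs 6% | 41% | 59% | 52% |
| 5% vs 10% | 66% | 34% | 29% |
| 7.5% vs 15% | 86% | 14% | 12% |
| 10% vs 20% | 95% | 5% | 4% |

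Chi-square with continuity correction gives almost the same results as Fisher's test (89% at 1% vs 2%, 34% at 5% vs 10%). With the 15% drop-out from section 11.2, 345 × 0.85 = 293 per arm, and Fisher's test misses 91% at 1% vs 2% and 42% at 5% vs 10%. If the section 11.6 adjustment covers safety tests, the miss rates rise further.

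**Step 4. What an interval would show.** With equal true risks *p* in both arms, the approximate half-width of the 95% interval for the risk difference is 1.96 × √(2*p*(1 − *p*)/345):

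- *p* = 1%: 1.96 × √(0.0198/345) = 1.5 percentage points
- *p* = 2%: 1.96 × √(0.0392/345) = 2.1 percentage points
- *p* = 5%: 1.96 × √(0.095/345) = 3.3 percentage points

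A doubling adds 1, 2 and 5 points respectively. If the observed risks are equal, the upper limit exceeds the doubling at 1% (1.5 > 1), just exceeds it at 2% (2.1 > 2), and lies below it at 5% (3.3 < 5). The interval separates these cases; three non-significant P values would look alike.

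**The case against.** Four objections carry weight.

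**This is analysis-plan detail.** Section 11.1 says the statistics are only summarised, with a detailed plan to follow, and that plan is not at hand. Effect measures and table layouts for safety are often left to it. Nor does the safety sentence rule intervals out, whereas section 11.1.1 does so expressly for baseline comparisons. This lowers the weight of the point but does not remove it. For safety the protocol is not silent: it names a method, and that method yields no estimate. If the analysis plan already adds intervals, only the protocol sentence needs aligning.

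**Tests are not the whole of the safety assessment.** Binary outcomes get a generalised linear model, which can give an estimate and an interval. Admissions and cardiovascular events are secondary outcomes, so they may come under it. The data monitoring committee reviews SAE reports. All of this stands, so it would be wrong to say that harm is examined by tests only. What remains is whatever falls under the safety sentence, and for the section 10.4 events that is unclear. Committee review is oversight during the trial, not a reported comparison.

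**The miss rates are assumed and are not caused by the sentence.** This is true. Rates of 1% to 5% and a doubling are illustrations, and some listed events may be commoner in women who all need treatment at randomisation. The miss rates come from sample size and rarity, and an interval leaves them unchanged.

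**Nobody says non-significance means safety.** A reader might infer that a non-significant test would serve as the trial's safety conclusion. The documents do not support that. No section says so, and the ethical statement in section 16.4 is not a safety hypothesis.

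**Conclusion.** The point holds as a minor one. Section 11.1.1 states the safety comparison as a significance test without an estimate or interval, unlike the primary outcome in the same section. At about 345 women per arm, such a test is weak for uncommon harms. Under the stated assumptions Fisher's test misses a doubling in 89% to 34% of trials for usual-care risks of 1% to 5% (uncorrected chi-square 82% to 29%). It performs adequately from about 7.5% upward.

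The consequence is limited to what the safety results can tell a reader. An interval would state the excess risk excluded, to within about 1.5 to 3.3 percentage points at risks of 1% to 5%; a P value does not. The conclusion rests on assumed event rates, a true doubling, full observation and unadjusted 5% tests. The test itself is a standard method and is not wrong.

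**What to change.** Amend the safety sentence in section 11.1.1 and carry the change into the analysis plan:

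- Report safety outcomes as the number and percentage of women with at least one event in each arm, with the between-arm risk difference and its 95% confidence interval (exact or score method for rare events).
- Keep Fisher's or chi-square P values as a supplement.
- State that a non-significant test will not be read as evidence that the arms are equally safe.
- State whether the section 10.4 events captured as outcomes fall under this sentence or under the generalised linear model for binary outcomes.

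The cost is a small text change and one more column in the safety tables, with no new data and no change to conduct. The downside is that intervals for rare events will be wide and will show openly that some excess risk cannot be excluded.

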11.1.2 Qualitative sub-study analysis

Interviews will be recorded, transcribed verbatim and de-identified. Interview and photographic data will be analysed using NVivo software. Analysis will be undertaken concurrently with data collection and conducted according to the standard procedures of rigorous qualitative analysis, which will include open and more focused coding, constant comparison and exploring deviant cases (Green, 2018). Analysis will be inductive, led by an experienced qualitative research fellow with close input from [name] and regular discussions with wider team members and PPI representatives. A range of theories will be used to interpret these data. These will include Normalisation Process Theory (Murray E, 2010), and theories relating to responsibilisation and the burden to treatment (May CR, 2014), ([name] L, 2021). Analysis will be used to iteratively develop an understanding of experiential and implementation barriers from the perspectives of participating women and healthcare professionals, and how self-management becomes embedded (or not) in both women's and healthcare professionals' routine work.

11.2. Sample Size Determination

Using data from the SNAP-HT feasibility trial and its follow-up study (Cairns AE, 2017), it is estimated that the standard deviation of mean daytime ambulatory diastolic BP at 6 months will be 10mmHg (inflated from 8mmHg to take into account greater heterogeneity between recruiting sites in this multicentre trial); 314 women (157 per group) are needed to detect ≥4mmHg difference (standardised difference 0.4) with alpha 0.05 and 90% power, and 15% post-randomisation drop out.

The aim will be to recruit approximately similar numbers of women with gestational hypertension/pre-eclampsia and chronic hypertension meaning that 628 women will be included overall. Assuming that the heterogeneity between these groups is small enough, 80% power will be retained for at least 5mmHg difference in diastolic BP for sub-groups of at least 40% of the total sample size, e.g. white vs non-white (expected 60:40 proportions). Furthermore, if appropriate to combine, the full sample of 628 women would allow smaller effect sizes to be detected (effect size = 0.22 - 80% power, effect size = 0.26 - 90% power).

During the regular monitoring of the trial, the TMG noted a higher proportion of gestational hypertensive women were enrolled in the study, (approximately 80%). In addition, the monitoring of ABPM completion showed low completion rates of ABPM (<50%). The sample size was subsequently inflated for operational reasons to retain the pre-specified power in the original sample size calculation in both gestational and chronic hypertensives as far as possible. Therefore, the sample size was updated to ensure 532 (266/0.5) gestational hypertensive women would be randomised and the remaining chronic hypertensive women to be recruited as far as possible in the recruitment period. Thus the recruitment period will allow approximately a total of 690 women.

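### Protocol section 11.2: the pooled detectable effects of 0.22 and 0.26 assume all 628 randomised women are analysed, and were not restated when the sample size was updated

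*Protocol*

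**What the plan says.** Protocol section 11.2 proceeds in three steps.

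- **Base calculation.** It takes the "standard deviation of mean daytime ambulatory diastolic BP at 6 months will be 10mmHg" and concludes that "314 women (157 per group) are needed to detect ≥4mmHg difference (standardised difference 0.4"). The conditions named for this figure are as follows: "with alpha 0.05 and 90% power, and 15% post-randomisation drop out". The 314 is the number to randomise in one diagnosis group.
- **Combined sample.** It plans similar numbers with gestational hypertension/pre-eclampsia and with chronic hypertension, "meaning that 628 women will be included overall". It adds that, if combining is appropriate, all 628 together could reveal smaller differences: "effect size = 0.22 - 80% power, effect size = 0.26 - 90% power".
- **Update.** Monitoring showed that about 80% of women enrolled were gestational hypertensives and that fewer than half completed ambulatory monitoring (ABPM). The gestational target was reset to 266/0.5 = 532 randomised. "Thus the recruitment period will allow approximately a total of 690 women". No pooled detectable effect is given for this design.

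Elsewhere, section 11.6 states "The level of significance will be set at 5% two-sided significance level", and section 9.7 sets 1:1 allocation. Section 11.3 restricts the primary analysis population to eligible participants with available data. Section 11.1.1 defines the primary estimand over all randomised participants, with diagnosis as an adjustment factor.

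**The concern.** The section treats 15% of women as lost when it sets 314 per diagnosis group. It then appears to count the same women as analysed when it says what 628 can detect. Both statements cannot describe one design.

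The update changes the total and the expected completion rate but leaves the pooled figures as they were. The primary estimand is the pooled comparison, and 0.22/0.26 are the only detectable effects given for it. A reader weighing a null result, or an estimate between 2 and 3 mmHg, would credit the trial with more power in that range than its own planning assumptions give.

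**Working it through.** **Inputs.** Two-sided 5% (section 11.6); 1:1 allocation (section 9.7); SD 10 mmHg, difference 4 mmHg, 90% power, 15% drop-out, 628 and 690 randomised, planning completion 0.5 (all section 11.2).

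**1. Base calculation.** Normal approximation, n per arm = 2 × (1.960 + 1.282)² / 0.4² = 131.3, so 132. The t-based search gives 133 per arm, or 266 in all. Then 133/0.85 = 156.5, rounded up to 157 per arm, or 314. This reproduces the protocol's 314. The update also uses 266 as the number needed with data, so 314 includes the drop-out allowance, and so does 628 = 2 × 314.

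**2. The stated pooled effects.** Detectable effect d = (1.960 + z) × 2/√N, where z = 0.842 for 80% power and 1.282 for 90%, and N is the total analysed.

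- N = 628: 5.603/25.06 = 0.224 and 6.483/25.06 = 0.259. These round to the stated 0.22 and 0.26.
- A one-sided test does not explain them. With 628 analysed it gives 0.198 and 0.234. With 534 analysed it gives 0.215 and 0.253, and 0.253 rounds to 0.25, not 0.26.

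Of the cases tried, only 628 women all analysed in a two-sided test matches both figures.

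**3. The same formula at the expected number analysed.**

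| Design | Analysed | 80% power | 90% power | Power at 0.22 | Power at 0.26 |
|---|---|---|---|---|---|
| 628, no loss | 628 | 0.224 | 0.259 | 79% | 90% |
| 628, 15% drop-out | 628 × 0.85 = 534 | 0.243 | 0.281 | 72% | 85% |
| 690, 50% completion | 690 × 0.5 = 345 | 0.302 | 0.349 | 53% | 68% |

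At SD 10 mmHg the second row is 2.4 and 2.8 mmHg, and the third is 3.0 and 3.5 mmHg. Relative to the first row the effects are larger by √(628/534) = 1.08 and √(628/345) = 1.35.

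**4. Lower completion.** The protocol reports completion below 50% but no exact rate. Assuming 40% to 45% of 690, between 276 and 310 women would be analysed, with effects of 0.34 to 0.32 at 80% power and 0.39 to 0.37 at 90%. This range is an assumption.

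**5. The 4 mmHg target.** Power = Φ(0.4 × √N/2 − 1.960). With N = 345: Φ(3.715 − 1.960) = 96%. With N = 266 gestational women: Φ(3.262 − 1.960) = 90%.

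**The case against.** The quoted sentence is a conditional remark, no sample size rests on it, and it names 628 as its basis. It belongs to the calculation made before the low ABPM completion was seen, so it cannot be blamed for not foreseeing it. This stands, and it is why the two parts should be kept apart. The drop-out part is a small inconsistency within the original calculation: 0.02 in standardised units, or 0.2 mmHg. The completion part is an omission in the update. But the condition in the sentence concerns whether the groups may be combined, not whether the data are complete, so it does not excuse leaving out the 15%.

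A reader might treat 345 as the most that can be analysed. The document does not support that. The rate below 50% was seen during monitoring, section 9.8 offers a repeat when too few readings are collected, and Appendix C records changes to the ABPM process and a wider follow-up window. Final completion could fall on either side of 50%; 345 is a planning value, taken from the protocol's own factor of 0.5.

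The planned model adjusts for the minimisation factors and may gain precision. That is a fair caveat, but the protocol does not quantify it, and 0.22/0.26 follow from 628 without it. To restore those figures with 345 analysed, adjustment would have to remove 1 − 345/628 = 45% of the outcome variance.

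**Conclusion.** The pooled detectable effects are wrong for the design that section 11.2 describes. Under its 15% drop-out they should be 0.24 and 0.28. Under the updated plan they are about 0.30 and 0.35. These values assume an unadjusted two-sample comparison, two-sided 5%, SD 10 mmHg and, for the update, exactly 50% completion.

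A reader might infer that the trial as a whole is less sensitive than claimed, or is underpowered for its primary comparison. The document does not support that. The 4 mmHg target was set with drop-out included, the gestational target was re-inflated for low completion, and power at 4 mmHg is about 96% pooled with 345 analysed and about 90% with 266 gestational women analysed. The overstatement is confined to what the pooled sample can detect below that target.

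**What to change.** In section 11.2:

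- Replace 0.22 and 0.26 with 0.24 (80% power) and 0.28 (90% power), stated for 628 women randomised with 15% drop-out, about 534 analysed.
- After the update, add that 690 women at the 50% planning completion rate give about 345 analysed and pooled detectable effects of about 0.30 and 0.35 (3.0 and 3.5 mmHg), before any gain from covariate adjustment.
- Note that observed completion was below 50%, and label any figure for a lower rate as an assumption.
- State that the 4 mmHg target keeps about 96% pooled power with 345 analysed.

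The cost is wording only. Recruitment, target difference and analysis do not change; the pooled figures become less favourable.

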3. SYNOPSIS

Study Title	Randomised Controlled Trial of Self-management of Postnatal Antihypertensive Treatment
Internal ref. no. / short title	SNAP2
Study registration	ISRCTN: 11042045
Sponsor	University of Oxford Research Governance, Ethics and Assurance, [name]
Funder	NIHR Programme Grant for Applied Health Research
Study Design	Multicentre randomised controlled trial

Study Participants	Women in the postn	atal period, requiring antihyperte	nsive treatment
Sample Size	At least 532 women with gestational hypertension resulting in a total, including with women with chronic hypertension, of approximately 690		
Planned Study Period	April 2024 - January 2027		
Planned Recruitment period	April 2024 - November 2025		
	Objectives	Outcome Measures	Timepoint(s) of evaluation of this outcome measure (if applicable)
Primary	To evaluate whether self- management of postnatal hypertension leads to lower diastolic blood pressure	Mean daytime ambulatory diastolic blood pressure	22-39 weeks
Secondary	To evaluate whether self- management of postnatal hypertension leads to lower systolic blood pressure	Mean daytime ambulatory systolic blood pressure	22-39 weeks
	To assess nocturnal ambulatory clinic blood pressure	Mean 24 hour and nocturnal ambulatory blood pressure	22-39 weeks
	To assess clinic or at home measured systolic and diastolic blood pressure	Systolic and diastolic blood pressure at follow up (mean of 2nd/3rd readings and mean of 2nd – 6th readings) measured in clinic or at home.	Baseline ¹ 6 weeks 12 weeks 22-39 weeks 48-60 weeks
	To assess participant reported health-related quality of life and anxiety associated with self-management of blood pressure	Maternal health-related quality of life (EQ-5D-5L health questionnaire results)	Baseline 6 weeks 12 weeks 22-39 weeks 48-60 weeks

¹ Baseline readings taken from maternity notes)

	in the postpartum period.		
	To assess anxiety	Short form anxiety inventory questionnaire	Baseline 12 weeks 48-60 weeks
	To assess medication adherence	Presence of urinary antihypertensive metabolites	6 weeks Baseline
		MARS questionnaire	6 weeks
	To assess if BP self- management postpartum can reduce postnatal readmissions to hospital associated with hypertension	All cause admissions Pregnancy hypertension admissions Cardiovascular events	Records review at end of trial period

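### The revised sample size cannot retain the pre-specified power in chronic hypertension: about 42% at 50% ABPM completion, against the 90% originally planned, and section 11.2 does not say so

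*Protocol*

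**What the plan says.** Protocol section 11.2 first sizes one comparison: 314 women (157 per arm) to detect 4 mmHg, SD 10 mmHg, "with alpha 0.05 and 90% power, and 15% post-randomisation drop out". It then plans similar numbers of gestational hypertension/pre-eclampsia and chronic hypertension, 628 in all, so that each diagnosis group is sized at 90%. For the full 628 it gives detectable standardised effects of 0.22 (80% power) and 0.26 (90% power), on the condition "if appropriate to combine".

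The next paragraph reports that about 80% of recruits were gestational and that monitoring "showed low completion rates of ABPM (<50" per cent). The sample size was therefore inflated "to retain the pre-specified power in the original sample size calculation in both gestational and chronic hypertensives as far as possible", and "the sample size was updated to ensure 532 (266/0.5) gestational hypertensive women would be randomised". Chronic women have no numerical target. The synopsis gives the result: "At least 532 women with gestational hypertension resulting in a total, including with women with chronic hypertension, of approximately 690".

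Section 11.1.1 defines the primary estimand over all randomised participants and fits one model, with principal diagnosis as an adjustment factor. Principal diagnosis is also one of the pre-specified subgroup analyses of the primary outcome. Section 11.6 sets the level: "The level of significance will be set at 5% two-sided significance level".

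**The concern.** The revision names both diagnosis groups as groups whose planned power is to be kept, but only the gestational group receives a number that could keep it. The chronic group gets whatever is left of an approximate total, and no power is quoted for it. A reader who takes section 11.2 at its word could treat a null result in the chronic subgroup as informative about a 4 mmHg effect, when the trial would have had well under an even chance of detecting one.

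Two other parts of the section need attention. Dividing 266 by 0.5 leaves no margin when the rate just reported is below 50%. And the only figures for the pooled analysis, which is the primary one, still refer to 628 women with complete data. The power of the planned primary analysis at the revised size is stated nowhere in the protocol.

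**Working it through.** **Inputs.** Difference 4 mmHg, SD 10 mmHg (d = 0.4), 90% power and 15% drop-out (section 11.2); 5% two-sided (section 11.6); 1:1 allocation (section 9.7); 532 gestational and about 690 in total (section 11.2 and synopsis). The chronic number is obtained by subtraction: 690 − 532 = 158. The actual completion rate is not given beyond being below 50%, so 50%, 49%, 45%, 40% and 35% are used as assumptions, applied equally to both diagnosis groups.

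**Method.** Two-sample t-test with n women with data per arm and noncentrality 0.4 × √(n/2). The normal approximation is Φ(0.4 × √(n/2) − 1.96).

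**Reproducing the plan's figures.**
- 90% power at d = 0.4 needs 132.3, so 133 per arm, or 266 with data.
- 133/0.85 = 156.5, so 157 per arm, or 314. This matches.
- 266/0.5 = 532. This matches.

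**Chronic group.** 158 × 0.5 = 79 with data, 39.5 per arm, against 266 needed. Noncentrality = 0.4 × √19.75 = 1.78. The normal approximation gives Φ(−0.18) = 43%; the t-test gives 41.9%. The difference detectable with 90% power is about 7.4 mmHg. If chronic women are instead 20% of 690 (138), power at 50% completion is 37%.

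**Gestational group.** 532 × 0.5 = 266, 133 per arm. Noncentrality = 0.4 × √66.5 = 3.26, power 90.1%. At 49% completion it is 89.6%.

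**Pooled primary comparison.** 690 × 0.5 = 345, 172.5 per arm. Noncentrality = 0.4 × √86.25 = 3.71, power 96%. The 266 women needed for 90% are 266/690 = 38.6% of the total, so power stays at 90% down to about 39% completion.

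Power for 4 mmHg (SD 10, t-test):

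| ABPM completion | Pooled (690) | Gestational (532) | Chronic (158) |
|---|---|---|---|
| 50% | 96% | 90% | 42% |
| 45% | 94% | 87% | 38% |
| 40% | 91% | 83% | 35% |
| 35% | 87% | 77% | 31% |

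**Pooled detectable effects.** d = 2 × (1.96 + z)/√N, with z = 0.842 for 80% power and 1.282 for 90%.
- N = 628: 5.60/25.06 = 0.22 and 6.48/25.06 = 0.26. These match section 11.2, so they assume that all 628 women provide data.
- N = 628 × 0.85 = 534, the section's own drop-out rate: 0.24 and 0.28.
- N = 690 × 0.5 = 345: 5.60/18.57 = 0.30 and 6.48/18.57 = 0.35.

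**The case against.** The sentence is hedged: it promises power only so far as is possible, sets no chronic target, and openly reports the 80:20 mix and the low completion. It does not claim 90% outright. That stands, and it limits the charge to a stated aim that one group cannot come near to meeting, with the shortfall not quantified. A fall from 90% to about 40% is still too large for the hedge to convey.

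The gestational criticism is conditional. The figure of 0.5 is a planning value and the target is worded as a minimum. The protocol has steps that could raise completion: repeat monitoring, remote fitting support, a voucher and a 22-39 week window. The SD was also inflated from 8 to 10 mmHg; at 8 mmHg gestational power is 95% even at 40% completion. All this stands, so no definite gestational shortfall can be asserted. At SD 8 the chronic group still has only about 59% power at 50% completion.

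Two stronger readings are tempting. The first is that the trial as a whole is underpowered. It is not: section 11.1.1 makes the pooled comparison primary, and that keeps at least 90% power down to about 39% completion. The second is that the words "if appropriate to combine" let the primary test be chosen after the data are seen and so inflate the type I error. The protocol describes no such procedure. Section 11.1.1 fixes one pooled model, section 11.6 promises adjustment for multiple comparisons, and the phrase sits in the account of the 628-woman design. It is a loose end between two sections, not an analysis rule.

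**Conclusion.** Wrong as written for chronic hypertension. On the protocol's own inputs, power there is about 42% at 50% completion and lower at any rate below that. This rests on about 158 chronic women, a subtraction from an approximate total, and on SD 10 mmHg with an unadjusted comparison; the planned covariate adjustment could raise power somewhat, but the documents give nothing with which to size the gain. The gestational target meets 90% only if completion reaches 50%. Just below that the loss is trivial, but it is 3 points at 45% and 7 points at 40%. The pooled detectable effects of 0.22 and 0.26 do not apply at the revised size and completion. The primary comparison is sound for 4 mmHg, so the defect lies in what section 11.2 says about power, not in the viability of the trial.

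**What to change.** Amend section 11.2 as follows:

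1. Replace the retained-power sentence and the 0.22/0.26 figures with pooled, gestational and chronic power for 4 mmHg over completion of 35% to 50%, as in the table above, and with the pooled detectable effects at the revised size (0.30 and 0.35 at 50% completion). Give the completion rate actually observed.
2. State that the trial is powered for the pooled comparison of section 11.1.1, and that the chronic group will be reported as an estimate with a confidence interval from the diagnosis-by-arm term.
3. Delete "if appropriate to combine", so that section 11.2 agrees with the single pooled primary model.

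The cost is protocol wording and a less favourable stated subgroup power. Recruitment and the primary analysis do not change.
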